2.3 Potential Risks and Benefits

2.3.1 Potential Risks

The risks of SCOUT localization are similar to or less than wire localization: bleeding, injury to vessels, adjacent tissue injury, pain, infection and repeating the procedure.

The most significant risk for this study is if the surgeon may not be able to successfully excise the device and/or target lesion. This has not occurred to date in our clinical (>150 patients) experience at MHS with our experienced breast surgeons.

Another potential risk to the patients is that the SCOUT device(s) might move during the 31-365 day time period. This could possibly require a longer procedure to remove the lesion(s) and/or retrieve the device(s). This has occurred to date in our clinical experience in less than

1% of our initial 150 patients, which is less than the device risk of wire migration (2 - 3%) which has been reported in the US for over 30 years.

Furthermore, standard wire localization procedures may require a second surgery to re-excise and get clear margins. Standard wire localization re-excision rate is reported by the American Society of Breast Surgeons as 20 - 40% nationally. However, the rate of positive margins with SCOUT localization is non-inferior or better than wire localization (1).

2.3.2 *Potential Benefits*

If long-term SCOUT device(s) localization is successful, neo-adjuvant therapy patients should be able to avoid some of the common and costly limitations associated with standard localization. After neo-adjuvant therapy, lesions are incompletely visualized for targeting. This can lead to: multiple additional pre-operative procedures, more complex and costly MR-guided procedures, and additional surgical procedures to fully excise the target lesion(s). We believe that use of the SCOUT localization procedure might lead to improved excision of the targeted tumor bed, fewer breast procedures, a reduced need for additional operations for margin re-excision and more convenience for the patient, operating room, surgeon, and radiologist scheduling. This will result in lower costs. In addition, the non-wire SCOUT offers surgeons more surgical access options for improved oncologic and cosmetic results (1).

2.3.3 *Minimization of Risks*

IRB approval is required prior to screening and enrollment. Subjects are required to provide signed informed consent prior to participation.

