In the event that the SCOUT device is not detected over 31 - 365 days, we have an existing standard of care safety net procedure to use an additional localization device at no charge to the patient (via a second SCOUT device placement and/or standard wire localization).

Patients will be scheduled for their standard of care preoperative imaging 0 – 30 days prior to the scheduled surgery for the radiologists to perform skin marking (standard of care). At that visit, the radiologists will use the SCOUT system to verify that the SCOUT device(s) is detectable from the skin. If the radiologist cannot detect the device(s) at the target, this will be immediately communicated to the surgeon who will determine whether to request an additional SCOUT device(s) or standard wire localization *at no additional cost* to the patient. Although the patient will end up with the standard of care procedure, a slight increased procedure time might occur since the first SCOUT device(s) will need to be removed in addition to the subsequent localization device. We anticipate this risk to be less than 1% (1/150 patients), which is less than routine standard of care (2 - 3%) pre-operative wire localization migration. Vasovagal risks that occur with standard of care pre-operative wire localizations (2 - 3%) have not occurred in our 150 patient experience with SAVI SCOUT. Subjects will be instructed to contact the study investigators about device-related issues. These issues will be promptly communicated to the study investigators for reporting as needed.

2.3.4 *Justification for Conducting the Study*

Risks to the subjects associated with this study are low. SAVI SCOUT is used routinely by the surgeons participating in this study in this population. The vast majority of these subjects would receive one or more SAVI SCOUT device(s) prior to surgery. The overall increase in risks to the subjects is small and they may benefit from the improved accuracy of identifying the target lesion(s) for surgical excision. This benefit is anticipated to exceed the rare potential instances of device migration or inability to locate the device(s).

In order to protect the privacy of study participants, all study data will be restricted to password protected computers and servers on the protected MHS and Envision Physician Services (formerly Sheridan) networks. Any study data will be de-identified before being sent to a third party.

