5.6 Subject Withdrawal

5.6.1 Withdrawal Procedures

Subjects are free to withdraw from participation in the study at any time upon request. An investigator may terminate a study subject's participation in the study if:

- Any clinical adverse event (AE), laboratory abnormality, or other medical condition or situation occurs such that continued participation in the study would not be in the best interest of the subject.
- The subject meets an exclusion criterion (either newly developed or not previously recognized) that precludes further study participation.
- The subject may elect to withdraw for any reason. However, the subject must either allow for needle-guided (non-surgical) removal by the radiologist or sign a release of records that allows the PI to validate surgical excision at an outside facility.

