7.2 Enrollment/Baseline (Study Visit 1 - 31-365 days prior to surgery)

- Patient has SAVI SCOUT LOCALIZATION by Radiologist at any time prior to neoadjuvant treatment SAVI SCOUT placed anytime FDA clearance 10/31/17
- Verify inclusion/exclusion criteria.
- Surgeon and/or MCI research nurse/Investigator
 - complete the **Patient Inclusion/Exclusion Eligibility Enrollment Form**.
 - obtain **consent** from subject on **Informed Consent Form**: Before or after SAVI SCOUT LOCALIZATION and PRIOR TO NACT
 - complete **the Documentation of Consenting Process Form**
- **Research Radiologist**
 - Verifies inclusion/exclusion criteria and Assigns Study ID
 - Completes Device(s) Placement Form
 - *Sends Copy of Consent and Study ID sent to OHR for tracking.*

Sometimes, additional studies ordered by Med-Onc can impact surgical plan.

7.3 Device Placement and Post-Implant Verification (Study Visit 2, Day 0-30 days prior to surgery)

**Breast Radiologist completed standard of care pre-operative skin marking*

Research Radiologist

Completes the Device Placement Form [Device Placement Recheck]] on standard of care imaging and performs audio verification and repeat skin marking if requested as standard of care by surgeon.

If not verified, the surgeon must be notified to determine whether the patient must be scheduled for a second localization procedure 0 - 365 days prior to surgery.

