8.2 Time Period and Frequency for Event Assessment and Follow-Up

Unanticipated problems will be recorded in the data collection system throughout the study.

The PI will record all reportable events with start dates occurring any time after informed consent is obtained **until 30 days** (for non-serious AEs) or 7 days (for SAEs) after the last day of study participation. At each study visit, the investigator will inquire about the occurrence of AE/SAEs since the last visit. Events will be followed for outcome information until resolution or stabilization.

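### The event-recording window in section 8.2 runs from the end of participation, not from device removal, so late non-serious device effects may be missed in a subject the investigator terminates with the device still implanted

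*Combined protocol and SAP*

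**What the plan says.** Section 8.2 sets the recording window for reportable events. It opens at consent and closes 30 days (non-serious) or "7 days (for SAEs) after the last day of study participation". Neither limit refers to removal of the device. Active ascertainment is tied to visits: "At each study visit, the investigator will inquire about the occurrence of AE/SAEs since the last visit". The same section also says: "Unanticipated problems will be recorded in the data collection system throughout the study".

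After enrolment, the next visit is the pre-operative check in section 7.3 ("Study Visit 2, Day 0-30 days prior to surgery"). The surgical visit follows in 7.4 and the completion form in 7.5.

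Section 5.6.1 allows the investigator to end a subject's participation for an adverse event or another medical condition. It also allows it when "The subject meets an exclusion criterion (either newly developed or not previously recognized) that precludes further study participation". The only provision about the implanted device sits in the item on a subject who chooses to leave: "However, the subject must either allow for needle-guided (non-surgical) removal by the radiologist or sign a release of records". The stated purpose of the release is to confirm excision at an outside facility, not to collect events.

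Two other sections bear on this. Section 8.1.4 has device effects entered on case report forms and monitored over the whole study, with no end date. Section 8.1.5 says that serious adverse events, serious device effects and unanticipated adverse device effects (UADEs) are captured for the whole study. Section 4.1.2 makes the rate of device-related complications a secondary endpoint.

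**The concern.** The study is about a device that stays in for 31 to 365 days, so device effects should be collected for as long as the device is in the body. The window in 8.2 follows study participation instead. The two coincide for a completer, but can separate for a subject whom the investigator terminates during neoadjuvant treatment. She still carries the device, has no further study visit, and is not clearly covered by the removal or records-release step.

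Some grounds for termination are also related to the device. Suspected nickel allergy is an exclusion criterion (5.3), and the device contains a nickel-titanium wire (2.1). A new adverse event is itself a ground. It is therefore plausible, though not shown, that the subjects who leave this way differ in device risk from those who stay. At stake is the completeness of a safety endpoint, and follow-up of a small number of women with an implant.

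**Working it through.** The plan gives no figure to reproduce. The check sets the sections side by side and then bounds the effect.

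**1. Completer.** The device comes out at the surgical visit (7.4), which is the last scheduled visit. The 8.2 windows therefore reach at least 7 and 30 days past removal, however the 30 days in 7.5 are read. There is no gap.

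**2. Subject terminated by the investigator.** Let T be the days from termination to device removal. Neither T nor the number of such subjects is in the documents. Under 8.2 alone, the implanted days after the window closes are

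- non-serious: max(T − 30, 0)
- serious: max(T − 7, 0)

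| T (assumed) | Non-serious | Serious, if 8.2 governs | Serious, if 8.1.5 governs |
|---|---|---|---|
| 7 | 0 | 0 | 0 |
| 30 | 0 | 23 | 0 |
| 60 | 30 | 53 | 0 |
| 90 | 60 | 83 | 0 |

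The non-serious gap opens only when T exceeds 30. The pre-operative visit falls 0 to 30 days before surgery. With removal at surgery, this means a termination before that visit, so the subject misses the inquiry at both remaining visits.

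**3. Does other text close the gap?**

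- *Serious events.* Section 8.1.5 sets no individual cutoff and 8.2 sets 7 days. The two conflict, and the documents do not say which prevails.
- *All device effects.* Section 8.1.4 has no end date and no filter for seriousness, but does not say how a former participant is observed.
- *Unanticipated problems.* Reporting under 8.1.5 and 8.4.1 starts when the investigator learns of the event. The UADE definition needs a serious effect not already identified. Its list of examples includes pain, infection and bleeding, yet 2.3.1 gives these as known risks ("bleeding, injury to vessels, adjacent tissue injury, pain, infection and repeating the procedure"). A non-serious late case is not clearly covered.
- *Events already recorded.* Section 8.2 follows these to resolution or stabilization. That does not extend to new events.
- *Self-report.* Section 2.3.3 says: "Subjects will be instructed to contact the study investigators about device-related issues". This is passive.

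**4. Effect on the endpoint.** Assume one complication in such a subject is missed, there are no others, and she stays in the denominator. With exact (Clopper-Pearson) 95% limits, the upper limit for 0/n is 1 − 0.025^(1/n). For 1/n it is the p that solves (1 − p)^n + n·p·(1 − p)^(n − 1) = 0.025.

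| n | Event missed | Event recorded |
|---|---|---|
| 35 | 0/35 = 0%, upper limit 10.0% | 1/35 = 2.9%, upper limit 14.9% |
| 25 | 0/25 = 0%, upper limit 13.7% | 1/25 = 4.0%, upper limit 20.4% |

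The shift in the estimate is 1/n per missed event. It is zero if there is no such subject or no such event.

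**The case against.** The strongest reply is that the plan has its own rules for device effects. Sections 8.1.4 and 8.1.5 call for capture over the whole study, and the window in 8.2 applies to reportable events, a term it does not define. This stands in part. A reader might infer from 8.2 that serious device effects are lost after day 7. The documents do not support that, because 8.1.5 says otherwise. What remains for serious events is a conflict to resolve.

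A second reply is that completers are not asked about events between enrolment and the pre-operative visit either. This also stands. A reader might turn the uncovered days into a share of lost observation. With an assumed 150-day dwell and termination at its midpoint (T = 75), the non-serious figure would be 45/150 = 30%. That share does not measure lost ascertainment. The completer too is unobserved in the interval; what she has is a later question that looks back over it. The terminated subject loses that question, not continuous surveillance.

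Third, eligible subjects are to have excision within Memorial Healthcare System (MHS, 5.2). Pre-operative verification there is standard of care (2.3.3, 6.2.1), and medical records are the main data source (section 10). A terminated subject would probably be seen by the same service, so an effect may well come to light. But nothing requires it to be entered as study data after termination, and section 10 warns that standard reports may lack what the study forms hold.

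Finally, the removal or records-release sentence could be read as covering every departure, since it sits in the list of termination grounds. Its position in the item on elective withdrawal makes that the less natural reading.

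**Conclusion.** The gap is real, narrow and minor. For it to matter, the investigator must end participation more than 30 days before removal. A new non-serious or already-known device effect must then start after the window closes, and neither the subject nor her clinicians must bring it into the study record. The documents give no number for such terminations, and it may be zero. The illustrated effect is one event, and no threshold or decision rule in the plan depends on it. For serious events the finding is only that 8.1.5 and 8.2 disagree.

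The conclusion assumes that the last day of participation, which 8.2 does not define, is the termination date for a terminated subject. That follows from 5.6.1, which speaks of terminating participation. It is worth correcting because it concerns women who still carry the device and a named safety endpoint, and the correction is cheap.

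**What to change.** - **Section 8.2:** record device effects, serious or not, until the later of the current window or 30 days after confirmed device removal. This also removes the conflict with 8.1.5 for serious device effects.
- **Section 5.6.1:** apply the removal or records-release step to investigator terminations as well. Accept planned excision at MHS as a further route, so that a device still needed for guidance is not taken out.
- **Ascertainment:** with the subject's consent, check for device effects at her routine pre-operative visit and at surgery, or from the released records if surgery is elsewhere.

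The cost is wording in two sections and the consent form, plus slight form or chart-review work. No new visit or procedure is needed. A subject who refuses further contact or access to her records would remain unobserved.

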8.3 Characteristics of an Adverse Event

8.3.1 Relationship to Study Intervention

To assess relationship of an event to study intervention, the following guidelines are used:

8.3.1.1 Related (Possible, Probable, Definite):

- The event is known to occur with the study intervention.
- There is a temporal relationship between the intervention and event onset.
- The event abates when the intervention is discontinued.
- The event reappears upon a re-challenge with the intervention.

8.3.1.2 Not Related (Unlikely, Not Related):

- There is no temporal relationship between the intervention and event onset.
- An alternate etiology has been established.

8.3.2 Expectedness of SAEs

The PI will be responsible for determining whether an SAE is expected or unexpected. An adverse event will be considered unexpected if the nature, severity, or frequency of the event is not consistent with the risk information previously described for the intervention.

8.3.3 Severity of Event

The following scale will be used to grade adverse events:

- Mild: no intervention required; no impact on activities of daily living (ADL).
- Moderate: minimal, local, or non-invasive intervention indicated; moderate impact on ADL.
- Severe: significant symptoms requiring invasive intervention; subject seeks medical attention, needs major assistance with ADL.

8.4 Reporting Procedures

8.4.1 Unanticipated Problem Reporting to IRB

Incidents or events that meet the criteria for unanticipated problems require the creation and completion of an unanticipated problem report form. The following information will be captured when reporting an adverse event, or any other incident, experience, or outcome as an unanticipated problem to the IRB and to the study sponsor to evaluate regarding FDA reporting guidelines:

- Appropriate identifying information for the research protocol, such as the title, investigator's name, and the IRB project number.
- A detailed description of the adverse event, incident, experience, or outcome.
- An explanation of the basis for determining that the adverse event, incident, experience, or outcome represents an unanticipated problem.
- A description of any changes to the protocol or other corrective actions that have been taken or are proposed in response to the unanticipated problem.

To satisfy the requirement for prompt reporting, unanticipated problems will be reported using the following timeline:

- Unanticipated problems that are serious adverse events will be reported to the IRB, Monitor and study sponsor within 1 week of the investigator becoming aware of the event.
- Any other unanticipated problem will be reported to the IRB, Monitor and study sponsor within 2 weeks of the investigator becoming aware of the problem.
- All unanticipated problems should be reported to appropriate institutional officials (as required by an institution's written reporting procedures), the supporting agency head (or designee), and study sponsor.

The study will adhere to monitoring consistent with CFR 812.46, which requires:

- (i) *Securing compliance.* A sponsor who discovers that an investigator is not complying with the signed agreement, the investigational plan, the requirements of this part or other applicable FDA regulations, or any conditions of approval imposed by the reviewing IRB or FDA shall promptly either secure compliance, or discontinue shipments of the device to the investigator and terminate the investigator's participation in the investigation. A sponsor shall also require such an investigator to dispose of or return the device, unless this action would jeopardize the rights, safety, or welfare of a subject.
- (ii) *Unanticipated adverse device effects.* A sponsor shall immediately conduct an evaluation of any unanticipated adverse device effect. A sponsor who determines that an unanticipated adverse device effect presents an unreasonable risk to subjects shall terminate all investigations or parts of investigations presenting that risk as soon as possible. Termination shall occur not later than 5 working days after the sponsor makes this determination and not later than 15 working days after the sponsor first received notice of the effect.

(iii) *Resumption of terminated studies.* If the device is a significant risk device, a sponsor may not resume a terminated investigation without IRB and FDA approval. If the device is not a significant risk device, a sponsor may not resume a terminated investigation without IRB approval and, if the investigation was terminated under paragraph (ii) of this section, FDA approval.

9. STATISTICAL CONSIDERATIONS:

Study Hypothesis: Placement of the SCOUT device prior to neoadjuvant treatment with biologic (hormonal) and/or chemotherapy allows for long-term localization of breast/axillary lesions targeted for surgical excision.

Main Objective: To show that the SCOUT device can be used over an extended time (up to 365 days) prior to surgery to successfully guide surgical excision of breast or axillary lesions in patients who undergo neoadjuvant therapy. Preliminary performance and safety information will be collected.

9.1 Sample Size Considerations

This is a pilot study. It is felt that up to 25 - 35 subjects will provide a reasonable estimate for the efficacy of the method.

9.2 Final Analysis Plan

Simple statistics will be used to evaluate the collected data as to the data elements listed in the primary and secondary endpoints.

10. SOURCE DOCUMENTS AND ACCESS to SOURCE DATA/DOCUMENTS:

MHS and Envision Physician Scientific Research (formerly Sheridan Scientific Intelligence) will maintain appropriate medical and research records for this study, in compliance with ICH E6, Section 4.9 and regulatory and institutional requirements for the protection of confidentiality of subjects.

The main source of data will be the electronic and/or physical medical records of our institution. In addition to basic demographic information, notes from the appropriate radiologic, surgical and pathology procedures will be accessed in order to complete the case report forms.

Note that the forms must be completed at the time of the relevant procedure by the study coordinator and/or investigator, since these data might not be captured in the standard reports.

Patient Inclusion/Exclusion Eligibility Enrollment Form
Device Placement Form
Device Excision Form
Unanticipated Adverse Device Event(s) Form(s)
Study Completion Form

De-identified (identified by study ID number only) copies of all medical images depicting the breast lesion and SCOUT device may be shared for scientific presentations. These images are necessary for complete analysis of the reasons if there is any possible failure of the detection of FDA cleared SCOUT system over a longer duration prior to breast and/or axillary lymph node surgery. These images include the following:

1. Diagnostic imaging
2. Image-guided device placement
3. Imaging of device verification (if available)
4. Additional localization imaging (if necessary)
5. Post-excision specimen radiograph

All DICOM images should be de-identified according to the guidelines specified by the NCI Cancer Imaging Archive. For details, see:

<https://wiki.cancerimagingarchive.net/display/Public/De-identification+Knowledge+Base>

11. ETHICS AND PROTECTION OF HUMAN SUBJECTS:

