3. HYPOTHESIS: Placement of the SCOUT device(s) prior to neoadjuvant treatment with biologic (hormonal) and/or chemotherapy allows for long-term localization of breast/axillary lesions targeted for surgical excision.

4. STUDY OBJECTIVES:

Main Objective: To show that the SCOUT device(s) can be used over an extended time (up to 365 days) prior to surgery to successfully guide surgical excision of breast or axillary lesions in patients who undergo neoadjuvant therapy. Preliminary performance and safety information will be collected.

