4.1 Study Outcome Measures

4.1.1 Primary Endpoint:

The primary endpoint of this study is successful surgery. Successful surgery (defined as one where the device(s) stays in place and can be removed successfully during surgery) when this device(s) is placed 31 - 365 days prior to surgery. Unsuccessful surgery is defined as one where the device(s) does not stay in place and/or cannot be removed successfully during surgery) when this device is placed 31 - 365 days prior to surgery.

4.1.2 Secondary Endpoints:

- Number of days prior to surgery (31 - 365) that the SCOUT device(s) is placed by the radiologist to localize the target breast / axillary tissue.
- Success rate of device(s) placement by radiologist (within 1 cm of the center of the target tissue).
- Success rate of SCOUT localization procedure(s) stability. The SCOUT should not migrate more than 5 mm between day 0 - 365 days pre-surgery. This is measured on routine mammogram and/or ultrasound.
- Rate of device(s) related complications.

5. STUDY ENROLLMENT AND WITHDRAWAL:

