5.2 Subject Inclusion Criteria

In order to be eligible to participate in this study, an individual must meet all of the following criteria:

- Patient is willing and able to provide informed consent. Patient SCOUT device(s) is placed as part of routine care or study at any time but before neoadjuvant treatment begins.
- Patient is female.
- Patient is between the ages of 18 and 90 years.
- Patient has breast cancer and will undergo neoadjuvant therapy and excision at Memorial Healthcare System.
- Patient is willing and able to comply with all study procedures and be available to follow-up for the duration of the study (1 - 13 months).
- Patient reads or understands English or Spanish.

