5.5 Treatment Assignment Procedures

In this pilot study, all patients will receive the same treatment assignment, i.e. lesion(s) localization with the SCOUT device(s) 31 - 365 days prior to surgery. Neoadjuvant treatment decisions will be determined by patient's medical oncologist.

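### The plan does not set surgical success against dwell time, and scores only patients who reach surgery, so a high overall rate would not by itself support use near 365 days

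*Combined protocol and SAP*

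**What the plan says.** The main objective, in Section 4 and again at the head of Section 9, is "To show that the SCOUT device can be used over an extended time (up to 365 days) prior to surgery" and, in doing so, "to successfully guide surgical excision of breast or axillary lesions in patients who undergo neoadjuvant therapy". Both places add that the performance and safety information is preliminary, and Section 9.1 calls the study a pilot.

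Section 4.1.1 defines the primary endpoint as successful surgery: the device stays in place and is removed at operation, having been placed 31-365 days before. The converse is also a kind of surgery: "Unsuccessful surgery is defined as one where the device(s) does not stay in place and/or cannot be removed successfully during surgery". Section 4.1.2 lists dwell separately: "Number of days prior to surgery (31 - 365) that the SCOUT device(s) is placed by the radiologist".

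The analysis plan in Section 9.2 is one sentence: "Simple statistics will be used to evaluate the collected data as to the data elements listed in the primary and secondary endpoints".

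Two provisions determine dwell. Section 5.2: "Patient SCOUT device(s) is placed as part of routine care or study at any time but before neoadjuvant treatment begins". Section 5.5: "Neoadjuvant treatment decisions will be determined by" the patient's medical oncologist.

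Section 5.6.1 foresees exit without study surgery: "the subject must either allow for needle-guided (non-surgical) removal by the radiologist or sign a release of records that allows the PI" to confirm excision elsewhere. Section 2.3.3 foresees a device that cannot be detected before surgery, with a second SCOUT or a wire as back-up and the first device also taken out.

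**The concern.** Whether the device still works after a long time in the breast or axilla is the study's own question. Three features of the plan leave the answer hard to read.

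- **Dwell is recorded but not linked to the outcome.** No section specifies success by dwell, fixes dwell bands or plans a number of long-dwell patients. A reader of the overall rate could not tell whether many, few or no patients tested the upper part of the range.
- **The endpoint exists only if there is an operation.** A patient whose device is withdrawn by needle because of a device problem is neither a success nor a failure as worded.
- **The endpoint scores position and removal, not guidance.** An index device that cannot be detected, has not moved, is backed up and is then removed meets the wording of success, although it did not guide the excision.

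The second and third features can only raise the reported rate.

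**Working it through.** **The plan's own figure.** Section 9.1 gives 25-35 subjects on judgement. It states no target rate, interval width, error level or dropout, so there is no calculation to reproduce. The checks below use exact (Clopper-Pearson) two-sided 95% limits; the level is my assumption.

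**1. What a failure-free result would exclude.** With 0 failures in n, the upper limit on the failure rate is 1 - 0.025^(1/n).

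| Group | n | Upper limit on failure |
|---|---|---|
| Whole study, low end | 25 | 13.7% |
| Whole study, high end | 35 | 10.0% |
| Long dwell (assumed) | 5 | 52.2% |
| Long dwell (assumed) | 10 | 30.8% |
| Long dwell (assumed) | 15 | 21.8% |

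The documents do not say how many patients will have long dwell, so the last three rows are a range and not a forecast.

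**2. How far an overall rate can hide a long-dwell problem.** Assume 35 patients, k with long dwell and true failure rate q, and the other 35 - k failing at 1/150. The value 1/150 is borrowed from Section 2.3.3, where it describes a device not detected at the target; using it as a short-dwell failure rate is an assumption.

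Expected overall success = 1 - [(35 - k)/150 + kq]/35.

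Chance of no failure in 35 = (1 - q)^k × (149/150)^(35 - k).

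| k | q | Expected overall success | Chance of no failure |
|---|---|---|---|
| 5 | 10% | 98.0% | 48.3% |
| 5 | 20% | 96.6% | 26.8% |
| 5 | 30% | 95.1% | 13.8% |
| 10 | 10% | 96.7% | 29.5% |
| 10 | 20% | 93.8% | 9.1% |
| 10 | 30% | 91.0% | 2.4% |

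For example, k = 5 and q = 20%: 1 - (30/150 + 1)/35 = 1 - 1.2/35 = 96.6%, and 0.8^5 × (149/150)^30 = 26.8%. Success in long dwell is 80% in that row. Setting the short-dwell failure rate to zero instead raises expected success by (35 - k)/150/35, which is 0.6 points for k = 5 and 0.5 for k = 10.

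**3. One device-related exit (assumed, all others succeed).** Left out: 24/24 or 34/34 = 100% (lower limits 85.8% and 89.7%). Counted as failure: 24/25 = 96.0% (79.6%) or 34/35 = 97.1% (85.1%). The documents give no rate for such exits.

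**4. Undetected but removed devices.** At the protocol's 1/150, the expected number is 25/150 = 0.17 or 35/150 = 0.23. The chance of at least one is 1 - (149/150)^25 = 15.4% or 1 - (149/150)^35 = 20.9%. Only those that had also not moved would count as successes as worded, so the case is rarer still.

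**The case against.** The strongest reply is that this is a small pilot. Its objective is followed at once by a statement that the information is preliminary, and Sections 2.1 and 2.2 describe placement up to 365 days as already cleared and standard of care. No clearance therefore rests on this rate, and a descriptive estimate is an acceptable product. That stands. It is met by limiting the conclusion to the dwell observed, not by asking for power or more patients.

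A reader might also infer that the plan commits to a single pooled rate and nothing else. The documents do not say so. Section 9.2 is too short to promise or exclude a breakdown, and dwell days are among the data it covers. What can be said is that no breakdown is specified.

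The masking figures depend on assumed long-dwell numbers and failure rates. That also stands. With 10 long-dwell patients failing at 20-30%, at least one failure would appear 91-98% of the time. Masking is a real risk mainly when long-dwell patients are few or the excess failure is moderate.

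A further inference is that a replacement device could be scored as if it were the index device, because Sections 6.1.1 and 7.3 mention second placement 0-365 days before surgery while Section 6.2.1 says up to 30 days. The wording conflicts, but the recheck that would prompt a second placement is itself set 0-30 days before surgery. Placement inside the 31-365 day window would normally require surgery to be postponed. This is a consistency point, not a source of bias once only index devices are scored.

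Finally, the summary lists extra localizations as a secondary endpoint, so undetected devices would be partly visible. That is true of the summary; Section 4.1.2 omits the endpoint.

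**Conclusion.** The concern holds in this form: as specified, a high overall success rate would not by itself support use near 365 days, because success is not shown against an uncontrolled dwell time and is defined only for patients operated on. The dwell display matters most. A failure-free study limits overall failure to 10.0-13.7%, but failure at long dwell only to 30.8-52.2% if 5-10 patients are there. Over the assumed grid, overall success of 91.0-98.0% is compatible with 70-90% success at long dwell, and the chance of seeing no failure runs from 2.4% to 48.3%. A single device-related exit would move the rate by 3-4 points. The undetected-device case is expected to be rare and will usually change nothing.

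The documents do not support the stronger reading that the study cannot inform long-term use. The dwell data are collected; the gap is in the stated analysis and denominator. The long-dwell numbers, the failure rates and the 95% level are assumptions.

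**What to change.** In Sections 4.1 and 9.2:

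1. List each patient's outcome against dwell days, one line per patient with the dwell of each index device (Section 5.1 expects about 20% of patients to have more than one). State that the conclusion is limited to the dwell range observed.
2. Score the index device(s) in all enrolled patients with a SCOUT placed. For the analysis, count as failure an exit or non-surgical removal whose recorded reason is a device problem. This should include malfunction and non-detection, not only adverse events judged related under Section 8.3.1, because Section 8.1.5 says device deficiencies are not adverse events. List all other exits by reason, with a worst-case sensitivity bound. For example, 2 such exits in 35 (assumed), with all others successful, give 33/33 = 100% (lower limit 89.4%) and a bound of 33/35 = 94.3% (80.8%).
3. Report the rate with an exact 95% confidence interval. Show separately the index devices that were undetected and needed a second localization, with a sensitivity analysis counting them as not successful.
4. Carry the additional-localization endpoint from the Protocol Summary into Section 4.1.2.

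Separately, reconcile Sections 6.1.1 and 7.3 with Section 6.2.1 on the timing of a second placement.

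The cost is protocol wording and one listing, with no extra patients. The case report forms are not in the documents, so confirm that they capture placement date, detection result at the recheck and reason for exit. The downside is a more modest conclusion and possibly a slightly lower reported rate.
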